consumed intact cannabis (e.g., cannabis-containing brownies) on drug test results or behavioral evaluation of performance impairment. The pharmacokinetics and associated pharmacodynamics of cannabis administered via vaporization and oral consumption are currently not well understood and need to be better defined in order to evaluate methods of determining whether or not an individual under the influence of cannabis is impaired.

4. Study Procedures

- a. Study design, including the sequence and timing of study procedures (distinguish research procedures from those that are part of routine care).

Protocol Overview. The proposed study will be conducted at the Johns Hopkins Behavioral Pharmacology Research Unit (BPRU). Participants will complete six outpatient drug administration sessions, each lasting approximately 10 hours and separated by at least 1 week. Participants will receive placebo and two active doses of cannabis via two different routes of administration: orally ingested (0mg, 10mg, 25mg) and inhaled vapor (0mg, 5mg, 20mg). Doses were selected based on prior research at the BPRU; the low active doses are expected to produce discriminative drug effects, but not impair performance, and the high doses are expected to produce both discriminative drug effects and performance impairment. Each dose will be administered to each participant using a within-subjects crossover design. Dosing will be clustered by route of administration (e.g., first three sessions will involve oral administration followed by three sessions of vaporization), and route of administration will not be blinded due to difficulties in estimating the exact time of drug effect onset following oral administration. The order of route of administration will be counterbalanced across participants, and the order of doses within each three-session cluster will be randomized. Research volunteers will be recruited until 20 participants have completed the study.

Participants. We will recruit and consent up to 50 research volunteers in order to obtain 20 study completers. We anticipate that some participants may drop out of the study before completion. Based on recent studies using similar methodology, it is estimated that we will need to enroll 30 participants to achieve 20 study completers.

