Cannabis Exposure. After baseline assessments are completed, participants will receive either an oral or an inhaled cannabis exposure. Cannabis will be obtained from the NIDA Drug Supply Program and prepared accordingly for the two routes of administration (see below). For ease of dose calculation, we will obtain cannabis containing approximately 10% THC by volume for active dose administration and placebo cannabis for the “0mg” dose conditions. Because most cannabis available for medical and non-medical use is high in THC and low in minor cannabinoid content, the cannabis used in this study will not contain more than a 3% concentration of cannabinoids other than THC (e.g. CBD, CBG, CBC). Cannabis dose assignment will be blinded in this study; however, route of administration will not be blinded due to difficulties in timing drug onset and peak effects across oral and inhaled cannabis for a double-dummy drug administration procedure.

Oral Administration. Participants will self-administer a brownie containing cannabis measured to produce THC exposure of 0, 10mg, or 25mg. Participants will receive each cannabis dose (one per session) in a randomized order on three consecutive sessions. Cannabis brownies will be prepared using individual baking trays for each dose. Baking will occur using a small oven located in the BPRU pharmacy and a commercial brownie mix. The mix will be prepared according to manufacturer’s instructions, with a measured dose of finely ground cannabis added to a portion the brownie batter mixture sufficient to make one cannabis brownie. The plant material will be pre-heated to decarboxylate THCA to free THC. We have prepared brownies individually in this manner for previous studies and verified that this preparation method ensures that target THC cannabis doses can be reliably achieved. Study participants and research staff will be blind to dose assignment. Participants will be provided with cannabis brownies and drinking water approximately 1 hour after finishing their standardized low-fat breakfast, and will be instructed that they need to consume the brownie within 5 minutes. The conclusion of cannabis brownie consumption will be considered the “0 hour” by which remaining protocol assessments will be scheduled.

Vaporization. Participants will inhale vapor produced from cannabis plant material measured to contain 0, 5mg, or 20mg THC. Vaporization will be achieved using The Volcano desktop vaporizing device (Storz &

Date: May 18, 2018

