Cannabis dose assignment will be blinded in this study, but route of administration will not. It is standard procedure for appropriate scientific control in studies evaluating dose effects of psychoactive drugs to blind dose assignment. Blinding of route of administration is not necessary and would be difficult to manage in this study given the immediacy of effects via inhaled routes and the unpredictable delay in drug onset effects following oral administration.

- d. Justification of why participants will not receive routine care or will have current therapy stopped.

Participants in this study will be healthy volunteers. Routine care for any medical illness that may arise during participation will not be affected.

- e. Justification for inclusion of a placebo or non-treatment group.

A placebo dosing session will be included to help interpret active drug effects on pharmacodynamic outcomes. Placebo dosing provides a control for expectancy effects on subjective reports and cognitive performance as well as non-pharmacological factors such as fatigue, hunger, and learning effects on performance tasks. Placebo dosing is standard for research studies involving evaluation of acute drug effects.

- f. Definition of treatment failure or participant removal criteria.

Date: May 18, 2018
Principal Investigator: [name]
Application Number: IRB00122849

This is not a treatment study. Participants may quit participation at any time of their own volition. The study investigators will discharge study participants for failing to attend their scheduled session, failure to follow the protocol requirements, or for other reasons not known at this time.

- g. Description of what happens to participants receiving therapy when study ends or if a participant's participation in the study ends prematurely.

This is not a treatment trial; there is no direct course of therapy related to the participant population being targeted. We are recruiting healthy adults with experience using cannabis and who are not seeking treatment for substance use problems. Should any report the desire for treatment they will be referred to appropriate community service centers. Premature termination of participation may result in the need to recruit additional research volunteers, but should have no impact on the study volunteer directly.

5. Inclusion/Exclusion Criteria

Participants will meet the following eligibility criteria:

Inclusion Criteria

1. Have provided written informed consent

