8. History of clinically significant cardiac arrhythmias or vasospastic disease (e.g., Prinzmetal's angina).
9. Abnormal EKG result that in the investigator's opinion is clinically significant.
10. Epilepsy or a history of seizures.
11. Enrolled in another clinical trial or have received any drug as part of a research study within 30 days prior to dosing.
12. Individuals who have a recent history of traumatic brain injury diagnosed by CT/MRI and have current sequela from prior brain injury, as determined by the study physician
13. Individuals with anemia

6. Drugs/ Substances/ Devices

- a. The rationale for choosing the drug and dose or for choosing the device to be used.

All cannabis will be obtained specifically for use in this study from the Federal Drug Supply System. For oral administration, brownies will be made by the BPRU pharmacy and will contain target THC doses of 0, 10mg, or 25mg, (e.g., 100 or 250mg of cannabis material that is approximately 10% THC by volume; or 250mg cannabis for which THC and other cannabinoids has been extracted). For vaporization, THC doses of 0, 5mg, and 20mg will be administered. Cannabis will be vaporized using a commercial vaporizer called The Volcano (Storz and Bickel, GmbH & Company (Oakland, CA). To preserve the blind, we will mix active and placebo cannabis so that the same amount of plant material is placed in the vaporizer at each session. For example, if we obtain cannabis with 10% THC, the placebo dose will contain 200mg cannabis for which THC and other cannabinoids has been extracted. The 5mg THC dose will contain 50 mg cannabis with 10% THC and 150mg cannabis for which THC and other cannabinoids has been extracted. The 20mg dose will contain 200mg cannabis with 10% THC. Selection of doses was conducted to balance participant safety and tolerability based on our previous experience, and to administer 2 active doses they are expected to produce subjective drug effects via each route of administration, but only one that produces significant impairment of performance ability. This will help test the sensitivity of the biological and behavioral assessments for detecting impairment versus discriminable drug effects. We have experience safely delivering acute cannabis doses within the range utilized in this study with healthy adult volunteers who are not frequent cannabis users.

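### Vapor loads are matched for plant mass to protect the dose blind, but no equal plant mass is stated for the brownies; the same filler rule should apply to them

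*Combined protocol and SAP*

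**What the plan says.** Section 4c states the blind for the whole study: "Cannabis dose assignment will be blinded in this study, but route of administration will not". The Oral Administration and Vaporization paragraphs of section 4a each repeat it for their own route: "Study participants and research staff will be blind to dose assignment".

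For vapor, section 6a says how this is done: "To preserve the blind, we will mix active and placebo cannabis so that the same amount of plant material is placed in the vaporizer". It then works an example at 10% THC. The placebo load is 200 mg of extracted cannabis and the high dose is 200 mg of active cannabis. For the low dose, "The 5mg THC dose will contain 50 mg cannabis with 10% THC and 150mg cannabis for which THC and other cannabinoids has been extracted". The Vaporization paragraph adds an opaque balloon, and placebo material that still gives visible vapor.

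For brownies, section 6a gives only a parenthetical example of the material used: "100 or 250mg of cannabis material that is approximately 10% THC by volume; or 250mg cannabis for which THC and other cannabinoids has been extracted". In section 4a, the recipe describes individual baking, "with a measured dose of finely ground cannabis added to a portion the brownie batter mixture sufficient to make one cannabis brownie". It reports that earlier work "verified that this preparation method ensures that target THC cannabis doses can be reliably achieved". Neither place mentions extracted filler in the low-dose brownie, an equal total plant mass, or a check that the three brownies look, taste or feel alike.

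**The concern.** Each participant eats all three brownies in three consecutive sessions, so each can compare them. If one brownie contains visibly or palpably less plant material, it carries a cue that has nothing to do with THC. The primary outcomes include the self-rated Drug Effect item, the DRE assessments (which the objectives call subjective) and cognitive and psychomotor performance. Section 4e relies on placebo sessions to control expectancy in self-report and performance, and that control works best when the brownies differ only in THC.

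The dose in question has a specific job. Sections 4a and 6a choose the low dose to be felt without impairing performance, so that the assessments can be tested on telling impairment from a merely noticeable drug effect. For the oral route, that test draws on low versus placebo and low versus high, the two comparisons that a lighter low-dose brownie would touch.

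**Working it through.** **Inputs.** Section 6a gives the oral THC doses (0, 10, 25 mg), the vapor THC doses (0, 5, 20 mg), potency of about 10%, and the example masses. Section 4a gives session spacing and the expected numbers (20 completers, about 30 enrolled).

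**Step 1: reproduce the plan's figures.** THC = active plant mass × 0.10; total plant mass = active + extracted.

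| Route and dose | Active (mg) | Extracted stated (mg) | THC (mg) | Total stated (mg) |
|---|---|---|---|---|
| Vapor placebo | 0 | 200 | 0 | 200 |
| Vapor low | 50 | 150 | 5 | 200 |
| Vapor high | 200 | 0 | 20 | 200 |
| Oral placebo | 0 | 250 | 0 | 250 |
| Oral low | 100 | none stated | 10 | 100, if no filler |
| Oral high | 250 | 0 | 25 | 250 |

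All THC doses reproduce. The vapor loads are equal. The oral totals are equal only if filler is used that the text does not mention.

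**Step 2: size of the difference if no filler is used.** 250 − 100 = 150 mg, so the low-dose brownie would hold 100/250 = 40% of the plant mass of either other brownie. The low/high ratio does not depend on potency p: (10/p)/(25/p) = 0.40. Of the three oral dose pairs, placebo–low (250 vs 100) and low–high (100 vs 250) would differ, and placebo–high (250 vs 250) would not.

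**Step 3: set that against the whole brownie.** The documents give no brownie weight. If it were 20 to 60 g (my assumption), 150 mg would be 0.15/20 = 0.75% down to 0.15/60 = 0.25% of what is eaten. The 40% describes plant material, not the brownie.

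**Step 4: opportunity to compare.** Sessions are "each lasting approximately 10 hours and separated by at least 1 week". Adjacent brownies are therefore at least 7 days apart, and the first and third at least 2 × 7 = 14 days apart.

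**Step 5: filler needed to match at the high-dose mass.** Filler = 25/p − 10/p. At 10% this is 150 mg, the amount already used in the low vapor load. If actual potency were 8% to 12% (assumed range), the matched total would run from 312.5 to 208.3 mg and the filler from 187.5 to 125 mg. THC per brownie does not change in any of these cases.

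**Step 6: material cost at 10%.** Extracted cannabis already planned per completer: 250 + 200 + 150 = 600 mg. Adding 150 mg gives 750 mg, or 25% more. For 20 completers: 20 × 150 mg = 3.0 g. For 30 enrolled: 30 × 150 mg = 4.5 g, an upper bound because some will leave before the low oral session.

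**The case against.** The strongest reply is that this is a silence and not a shown defect. The oral masses are an example and may list only the active material. The placebo brownie is set at the high-dose mass, which suggests that matching was in mind. Pharmacy instructions are not among the documents, so filler may already be used. This stands: the text does not show that any brownie is unmatched.

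Next, the vapor parallel is incomplete. Plant load may affect the vapor a participant sees, whereas in a brownie the cannabis is finely ground, stirred into commercial batter and baked. The sponsor could have judged matching unnecessary. That is a fair inference, but the plan does not give it as a reason, and the brownie verification that it reports concerns THC content only.

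Third, the cue would say little. Placebo and high dose have the same mass, so a participant who noticed an odd brownie would not learn from that alone which dose it held. Staff who knew the example masses could make the link, but only if they noticed a difference. Both active doses are also expected to be felt, so some functional unblinding is expected whatever the plant mass. This stands as well and limits how much a cue could add.

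A reader might infer that the oral blind is broken, or that the low-dose oral results are biased. The documents do not support either. They contain no evidence that the difference exists in practice, that anyone would notice it, or which way it would push the ratings.

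**Conclusion.** The concern holds as a gap in the blinding method. The plan equalises plant mass for one route, gives the blind as its reason, and states no equivalent for the other route, although it promises the same blind. On the condition that the example masses are total plant material, two of three oral dose pairs differ by 150 mg at 10% potency and one pair is matched. The possible effect is limited to subjective, DRE and performance outcomes in comparisons that involve the low oral dose. Cannabinoid concentrations, high versus placebo, and all vapor comparisons are unaffected. The size and direction of any bias cannot be derived from the documents; it is zero if the difference goes unnoticed or if filler is already used. The point is minor and is worth acting on because the remedy costs almost nothing.

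**What to change.** In section 6a and in the Oral Administration paragraph of section 4a, apply the vapor rule to the brownies: add extracted placebo cannabis so that every brownie has the same total plant mass, with the THC content of each unchanged. In the 10% example this means 150 mg of extracted material in the low-dose brownie; at other potencies the amount follows from the formula in step 5. If the brownies are already made this way, one sentence saying so is enough.

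The cost is a sentence in each of the two places, weighing and mixing filler for one brownie per participant, and about 3.0 g more extracted cannabis for 20 completers (at most 4.5 g for 30 enrolled). No visit, assessment or THC dose changes.
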